8.3. Exclusion criteria

- Signs of severe malaria (adapted from WHO criteria, see section 8.4)
- Patients not fulfilling criteria for severe malaria but with another indication for parenteral antimalarial treatment at the discretion of the treating physician
- Haematocrit <15% at screening (For Gambia, Rwanda sites only: For subjects ≥12 years – Haematocrit <20% at screening)
- Subjects who have received artemisinin or a derivative within the previous 7 days OR lumefantrine or amodiaquine within the previous 14 days OR mefloquine or piperaquine within the previous 30 days
- In applicable countries: use of seasonal malaria chemoprophylaxis (SMC) within the last 14 days.
- Acute illness other than malaria requiring systemic treatment
- Severe acute malnutrition (in Niger – only those patients with Severe Acute Malnutrition and complications requiring inpatient nutritional treatment will be excluded)
- Known HIV infection
- Known tuberculosis infection
- For females: post-menarche (For Gambia, Rwanda sites only: females who are pregnant, trying to get pregnant or are lactating)
- History of allergy or known contraindication to any of the study drugs, including neuropsychiatric disorders and epilepsy
- Previous splenectomy
- Enrolment in DeTACT in the previous 3 months
- Participation in another interventional study in the previous 3 months

8.4. Criteria for severe malaria

- Impaired consciousness (Glasgow Coma Scale, Blantyre Coma Scale)
- Prostration
- Respiratory distress (defined as maximal respiratory rate, by age)
- ≥2 convulsions in the past 24 hours
- Circulatory collapse
- Pulmonary oedema
- Abnormal bleeding
- Visible jaundice

- Haemoglobinuria (blackwater)
- Hyperparasitaemia (>10%)

9. PROCEDURES

Study procedures will be performed according to the schedule of assessments (Appendix 1). Potential patients will be screened. If eligible and they have agreed to enter the trial, they will be admitted to the hospital for at least 72 hours and continue to be followed up as outpatients on a weekly basis until Day 63 (9 weeks).

9.1. Informed consent

Full consent (and assent if required) will be obtained before any study specific enrolment procedures are conducted. It will be made clear from the outset that refusal to participate will not jeopardise subsequent antimalarial treatment.

The patient (or witness if illiterate) and/or the parent/guardian of a minor must personally sign and date the latest approved version of the informed consent form before any study specific procedures are performed. Written and verbal versions of the participant information and informed consent in the local language will be presented to the participants detailing no less than: the exact nature of the study; the implications and constraints of the protocol; the known side effects and any risks involved in taking part. It will be clearly stated that participation is voluntary and that the participant or guardian is free to withdraw from the study at any time for any reason without prejudice to future care, and with no obligation to give the reason for withdrawal.

The patient and/or parent/guardian will be allowed as much time as possible to consider the information and to take the opportunity to question the Investigator, or other independent parties to decide whether they will (or allow his/her charge to) participate in the study. As far as possible, no more than two hours should elapse between presentation and treatment either within or outside of the study. For sites where this time window is not sufficient to complete all study-related procedures required before treatment, local approval will be sought to increase the time allowed for pre-treatment procedures.

Written informed consent will be obtained by means of the participant's or participant's guardian's dated signature or thumb print (if unable to write), and the consent form must be signed and dated by a literate witness and dated signature of the person who presented and obtained the informed consent.

If required by local ethics committees, children will be asked to sign or affix a thumbprint on an assent form. A copy of the signed informed consent/assent document(s) will be given to the subjects/parents.

9.2. Screening procedures

Subjects who present at the participating sites will be screened to assess eligibility using the inclusion and exclusion criteria summarized in section 8.2 and 8.3.

A screening form will be completed for all subjects. A screening log will be kept.

EDTA-anticoagulated blood (0.5 ml) will be collected for:

- Parasite count from Giemsa stained thick and thin blood films with or without malaria rapid diagnostic test
- Haematocrit

(For Gambia, Rwanda sites only: After obtaining consent a urine pregnancy test for females of child bearing potential will be performed.)

9.3. Baseline assessments

9.3.1. Demographic and medical history

Basic demographic and epidemiological data (e.g. sex, age, address, bed net use, malaria risk factors, prior treatment and previous participation in this or previous studies), and a full medical history will be recorded by the study staff.

9.3.2. Drug history

All prescribed or over-the-counter and traditional medications used within the last 7 days will be sought and the available details recorded. Any drug allergies will be recorded.

9.4. Randomization and blinding

In Africa, subjects who fulfil all the inclusion criteria and have none of the exclusion criteria will be randomised in an ACT: TACT: TACT: ACT ratio of 1:2:2:1 with the ACT arms consisting out of an ACT and placebo.

The study drug will be provided by the pharmaceutical company in co-blistered or co-packed form in boxes.

The boxes containing artemether-lumefantrine+amodiaquine and artemether-lumefantrine+placebo will be identical, and a combination of both study drugs boxes will be sequentially numbered.

Also, the boxes containing artesunate-mefloquine+piperavaquine and artesunate-mefloquine+placebo will be identical, and a combination of both study drugs boxes will be sequentially numbered.

The absorption of lumefantrine is increased if the artemether-lumefantrine is taken with fat, which increases the efficacy. Therefore artemether-lumefantrine containing arms should be taken with fat.

The absorption of piperavaquine is also increased if it is taken with fat and can hence lead to increased prolongation of the QT/QTc interval. Therefore artesunate-mefloquine containing arms (with PPQ or PBO) should not be taken with fat.

For this reason it is important that the investigator knows whether the allocated treatment should be taken with a fatty snack or drink or not. Therefore the randomization envelope will state that

the allocated treatment potentially contains artemether-lumefantrine or artesunate-mefloquine. However it will not state whether a second partner drug (amodiaquine or piperaquine is included in the treatment). Furthermore the boxes containing either artemether-lumefantrine (+/- amodiaquine) or artesunate-mefloquine (+/- piperaquine) will be clearly distinguishable.

The subjects will be assigned a study arm through a computer-generated randomisation schedule. Individual, sealed and sequentially numbered envelopes will be provided for each trial site with one envelope per patient, indicating whether the treatment for the subject should be taken from the set of artemether-lumefantrine+/-amodiaquine or the artesunate-mefloquine+/-piperaquine containing set. Block randomisation will be used.

This study will be partially blinded since it will not be known to the investigators nor the participants at the time of randomisation or drug administration whether they have been assigned to an ACT or a TACT arm. However, they will know whether they have been assigned to the AL or ASMQ based arms for the reasons outlined above and also given the differences in dosing, i.e., 6 doses for AL based arms vs 3 doses for ASMQ based arms.

9.5. Clinical procedures

9.5.1. Clinical procedures at baseline

- Standardized symptom questionnaire
- Physical examination
- Weight, height, pulse, blood pressure, respiratory rate, temperature.
- Assessment of malnutrition status: Mid-Upper Arm Circumference (MUAC), presence and grading of (nutritional) oedema (if present)
- Spleen and liver size will be recorded if palpable.

9.5.2. Clinical procedures during hospitalization

Daily until day of discharge:

- Standardized symptom questionnaire
- Physical examination
- Pulse, blood pressure, respiratory rate
- Tympanic temperature (every 6 hours until two times <37.5 degrees Celsius)
- Recording of vomiting and retreatment
- Recording of adverse events

9.5.3. Place of residence, work, travel history and mobile phone use.

In order to have a greater understanding of the possible sites of malaria transmission, and to relate genetic diversity to geographical location, subjects or their guardians will be asked a short set of questions on their place of residence, place of work/location of school if applicable and their history of travel in the last 2 months. In addition, basic questions on use of mobile phones will be

asked. These questions will help in understanding the use of mobile phones in each country in subjects prone to malaria infections. In separate studies, we will use anonymised, aggregated data on mobile phone use to model population movement and predict potential routes of spread of malaria and antimalarial drug resistance. We will use the mobile phone usage survey to understand how relevant these movement patterns are to subjects with malaria.

We will review these travel histories obtained in the hospital and then select a representative sample of subjects for additional in-depth interviews with them and their peers to be conducted in their villages. This is to obtain a detailed understanding of the behaviours and risk factors for malaria infection.

In some sites, we will GPS the households of all subjects and their places of work and places where their infection may have occurred, such as forests, farms or plantations. We will collect all available local malaria treatment records to describe how the study population compares to the overall population who receive treatment for malaria and this will allow us to better understand local malaria epidemiology and transmission patterns. All personal information will be de-identified so that no individual can be identified from their treatment records, through interviews, or from mapping data.

9.5.4. Clinical procedures during follow up

Day 7, 14, 21, 28, 35 and 42

- Standardized symptom questionnaire
- Physical examination
- Pulse, blood pressure, respiratory rate
- Tympanic temperature
- Recording of adverse events

Day 49, 56 and 63

In principle follow up at day 49, 56 and 63 will consist only of performing a tympanic temperature measurement, blood smear and dried blood spot. If the subject indicates new symptoms and/or a positive blood smear is found the subject will be seen by the study clinician and the following will be performed.

At the Gambia, Rwanda sites only, a urine pregnancy test will be performed for women of child-bearing age at D63 only.

- Standardized symptom questionnaire
- Physical examination
- Pulse, blood pressure, respiratory rate
- Recording of adverse events

9.5.5. Clinical procedures in case of a recurrent infection

- Standardized symptom questionnaire
- Physical examination

- Weight, height, pulse, blood pressure, respiratory rate
- Tympanic temperature
- Completion of recurrent infection form
- Treatment of recurrent infection.
- Recording of treatment for recurrent infection in the concomitant medication form

Subjects with persistent asexual parasitaemia on day 7 or who develop a recurrent parasitaemia after day 7 with no signs of severity will be treated with either the same or another ACT or a different combination e.g. quinine and doxycycline or clindamycin, in accordance with local recommendations.

Subjects who develop a non-falciparum parasitaemia during follow up will be treated according to local guidelines.

In case of a recurrent infection, subjects should still be followed up according to the study protocol until day 63. An additional questionnaire on the place of living, work and travel and mobile phone use in the period between the initial infection and the recurrent infection will be completed.

9.5.6. Clinical procedures in case of unscheduled visits

Subjects presenting to the clinic with a fever or other clinical symptoms on unscheduled days will be assessed by the study physician. In any case the following will be recorded:

- Standardized symptom questionnaire
- Physical examination
- Pulse, blood pressure, respiratory rate
- Tympanic temperature
- Recording of adverse events

Subjects will be treated and further investigations conducted as clinically indicated.

In the event that a patient becomes pregnant, on study, additional visits will be added at 3 months, 6 months and 9 months (after birth), to allow documentation of the outcome of the pregnancy.

9.6. Electrocardiographic recording

Electrocardiograms (ECGs) will be recorded at D0H0, D0H4, D2H52 (for treatments containing ASMQ) or D2H64 (for treatments containing AL) and D42 in order to assess changes in the QT/QTc interval.

At the timepoint D0H4 and D2H52/D2H64 an abnormal automated electronic reading (QT or QTc-interval > 500 milliseconds) will be considered a Serious Adverse Event and will lead to discontinuation of the study drug but not discontinuation of the patient from the trial. A specific work instruction will describe procedures such as identifying other causes of QT/QTc prolongation, study drug replacement and follow up of the QT/QTc interval until normalization.

QT/QTc intervals will be measured every six hours after the first abnormal QT/QTc interval is recorded until the QT/QTc interval has normalized in two consecutive ECGs.

Additional blood samples will be taken for pharmacological measurements at the moment of the identification of the abnormal QT/QTc interval and 6 and 12 hours after the first identification of the abnormal QT/QTc interval in order to assess the correlation between the prolonged QT/QTc interval and the drug levels that could be leading to the prolonged QT/QTc interval.

9.7. Blood sampling

9.7.1. On admission/baseline

On study admission, immediately before drug administration, blood will be collected for the following:

- Repeat parasite count (thick and thin films). If it is found subsequently that this parasitaemia no longer meets the inclusion criterion for parasitaemia the patient will be kept in the study.
- Dry blood blots (200 microlitres, 4 spots collected on chromatography papers) for parasite and host genotyping (see section 14.3 for details on parasite genotyping and section 9.7.6 for details on host genotyping)
- Full blood count OR WBC differential, HCT, Hb (0.5 mL EDTA-anticoagulated)
- Parasite DNA and RNA measurements (packed cells from up to 5 ml for child, 10 mL from subjects ≥ 12 years in Gambia, Rwanda only) EDTA-anticoagulated blood; an aliquot of plasma will be stored for immunological assessments.
- *Ex vivo/in vitro* parasite cultivation for drug sensitivity and transcriptomic assays (2 ml child, heparinised blood, some sites; 3 mL from subjects ≥ 12 years in Gambia, Rwanda only).
- Baseline biochemistry assessments including bilirubin, ALT, AST, Alkaline Phosphatase and creatinine levels (1 mL heparin)
- Baseline Pharmacological measurement (1 mL heparin)

9.7.2. During hospitalization

Blood smears and haematocrit

Subjects with a parasite density of >5000 per μL will have blood taken for malaria films at 6h, 12h, 18h, 24h and thereafter every 12 hours until parasite clearance (when two consecutive malaria slides are negative).

In all cases, malaria films and haematocrit measurements will be performed at H24, H48 and H72 on all subjects (even if two consecutive negative blood smears have been seen before these timepoints).

Other sampling during hospitalization

- D0 H6, Day 0 H12: Parasite DNA/RNA measurements: EDTA-anticoagulated blood (1 mL). (some sites)
- Day 1 H24: Hct measurement (0.5 mL EDTA-anticoagulated)
- Day 1 H24: Parasite DNA/RNA measurements & qPCR: EDTA-anticoagulated blood (1 mL). (some sites)
- Day 2 H48: Hct measurement (0.5 mL EDTA-anticoagulated)
- D2 H48: For qPCR: EDTA-anticoagulated blood (1 mL). (some sites)
- D2H52 (for artesunate-mefloquine based arms) OR D2H64 (for artemether-lumefantrine based arms) – Pharmacological measurement sample (1 mL Heparin)
- Day 3 H72: biochemistry assessments including bilirubin, ALT, AST, Alkaline Phosphatase and creatinine levels: 1 mL heparinised blood
- Day 3 H72: For qPCR: EDTA-anticoagulated blood (1 mL). (some sites)
- Day 3 H72: Full blood count OR WBC differential, Hct and Hb. (0.5 mL EDTA-anticoagulated)

9.7.3. Blood sampling during follow up

Day 7

After subjects are discharged, they will be followed up at Day 7 for:

- Day 7: Malaria blood slide
- Day 7: Full blood count OR WBC differential, Hct and Hb (0.5 mL, EDTA-anticoagulated blood)
- Day 7: DNA/RNA for qPCR, gametocyte quantification and characterization: 0.5mL Heparin & 0.5 mL EDTA blood (For Gambia, Rwanda sites only, if performed: 1 mL each of Heparin and EDTA) (some sites)
- Day 7: Basic biochemistry assessments including bilirubin, ALT, AST, Alkaline Phosphatase and creatinine levels: 1 mL heparin blood
- Day 7: Pharmacological measurement (1 ml, heparin)

Day 14, 21, 28, 35 and 42

After day 7, subjects will be followed up weekly until Day 42 for:

- Malaria blood slide
- Day 14, 21, 28, 35 and 42: DNA/RNA for qPCR gametocyte quantification and characterization: (0.5 mL Heparin & 0.5 mL EDTA blood (For Gambia, Rwanda sites only, if performed: 1 mL each of Heparin and EDTA) (some sites)

- Day 28: Basic biochemistry assessments including bilirubin, ALT, AST, Alkaline Phosphatase and creatinine levels. (1 mL heparin blood)
- Day 28: Full blood count OR WBC differential, Hct and Hb (0.5 mL EDTA-anticoagulated)

Day 49, 56 and 63; Unscheduled visits

After day 42, subjects will be followed up weekly until Day 63 for:

- Malaria blood slide
- Dried blood spot

9.7.4. Blood sampling in case of a recurrent infection

Subjects with a recurrent falciparum parasitaemia (including mixed with another malaria species) during follow up will have blood taken for the following:

- Thick and thin films: parasite count.
- Dried blood spots (200 microlitres, 4 spots collected on chromatography paper) for parasite DNA genotyping
- Parasite DNA and RNA measurements (packed cells from up to 5 ml for child EDTA-anticoagulated blood; 10 mL from subjects ≥ 12 years in Gambia, Rwanda only); an aliquot of plasma will be stored for immunological assessments.
- *Ex vivo/in vitro* parasite cultivation for drug sensitivity and transcriptomic assays (2 ml child, heparinised blood, some sites; 3 mL from subjects ≥ 12 years in Gambia, Rwanda only).
- Pharmacological measurement (1 ml, heparin)

9.7.5. Blood sampling for pharmacokinetics

PK sampling (1 ml whole blood in heparin per sampling occasion). Venous plasma will be used to evaluate the drug exposures to antimalarial drugs used in this study (E.g. artesunate, artemether, lumefantrine, amodiaquine, piperazine, mefloquine, and their metabolites). A work instruction will be written to detail the technique for specimen collection, handling and storage. Samples will be centrifuged immediately and the plasma stored frozen at minus 80°C or lower in properly labelled cryotubes.

A maximum of seven samples for PK/PD analyses will be collected in each patient over a total sampling period of 42 days:

- One fixed day 0 sample will be collected for lumefantrine, amodiaquine, piperaquine, and mefloquine (and their metabolites) concentration measurements in all subjects.
- One sample will be collected systematically at the same time as the ECG at H52 (for ASMQ containing arms) and H64 (for AL containing arms)
- One fixed day 7 sample will be collected for lumefantrine, amodiaquine, piperaquine, and mefloquine (and their metabolites) concentration measurements in all subjects
- Two samples at random time-points during the first 3 days of dosing will be collected for artemether, artesunate, lumefantrine, amodiaquine, piperaquine, and mefloquine (and their metabolites) concentration measurements in 500 patients
- Two samples within random time windows during the 42 days of follow up will be collected for lumefantrine, amodiaquine, piperaquine, and mefloquine (and their metabolites) concentration measurements in 500 patients.
- In Niger only – three random samples during the first 3 days of dosing will be collected for artemether, artesunate, lumefantrine, amodiaquine, piperaquine, and mefloquine (and their metabolites) concentration measurements in all patients

Additional PK blood samples will be collected in the following situations:

- In case of an abnormal QT/QTc interval at H4, D42. A blood sample will be obtained at the moment of the first identification of the abnormal QT/QTc interval.
- At 6 and 12 hours after the first abnormal QT/QTc interval at any time-point (H4, H52, H64, D42) in order to assess the correlation between the prolonged QT/QTc interval and the drug levels that could result in a prolonged QT/QTc interval (maximum 3 ml heparin blood).
- In case of a recurrent infection at the day of recurrence (1 ml heparin blood).

9.7.6. Host genotyping

Genetic samples (in the form of dried blood blots or extracted DNA) will be stored (for a maximum of 10 years) and genotyped at the Molecular Tropical Medicine Laboratory, Bangkok, Thailand. Potential targets for targeted genotyping are polymorphisms in the G6PD genes coding for enzymes related to drug metabolism (e.g. cytochrome P450 enzymes) and genes and mutations predisposing to long QT-syndrome such as but not limited to the genes KCNQ1 (LQT1), KCNH2 (LQT2), and SCN5A (LQT3).

In case a particular genetic test cannot be performed at the Molecular Tropical Medicine Laboratory, Bangkok, Thailand, the genetic samples may be transferred to another institute (which might be a foreign country) for genotyping. The subject will be asked for consent for this

transfer during the initial informed consent process. A material transfer agreement will be in place when required before any samples are shipped.

The results of the genotyping will not be reported back to the subjects unless the abnormality is found through a method with a clear diagnostic certificate and the finding is judged to be of clear clinical or therapeutic importance to the subject.

9.8. Special procedures related to baseline biochemistry measurements

Screening is performed without assessing biochemistry values. At baseline blood will be drawn for biochemistry assessments just minutes before baseline drug administration. Initial treatment at baseline will therefore be administered without knowledge of the baseline biochemistry values. If baseline biochemistry values turn out to be abnormal (grade 3 or 4 of the CTCAE grading table) the study physician in consultation with the medical monitor will decide how to continue treatment and further management of the patient. In any case the subject will still be followed up according to the study protocol until day 63.

9.9. Time window for follow up visits

The time-window for the visit on Day 7 is + 1 day and for the visits on Days 14 - 63 is -1 to +2 days.

9.10. Blood volumes

The blood volumes for the protocol mandated tests are detailed in the study schedule (Appendix 1) and will vary slightly between sites depending on whether sites can perform all of the tests of this protocol e.g. not all sites will be able to do the full blood count, store the plasma PK samples or do the *ex vivo* parasite culture. Also, it is likely that only a minority of subjects will develop a recurrent parasitaemia and be requested to give further blood samples.

Concerning blood volumes, an age of 12 years and older will be referred to as 'adult', an age of less than 12 years will be referred to as 'child'.

Maximum blood volumes are presented below for 63 days of follow up. The maximum blood volume is the total amount taken if the subjects remained in hospital for 3 days, had all blood samples taken and where part of the pharmacokinetic as well as other subsets (like qPCR validation and sampling for gametocyte genetics) and had one recurrent parasitaemia and/or unscheduled visit during follow up. The maximum blood volume will be approximately **48.5 ml (66.5 mL** in subjects ≥ 12 years in Gambia, Rwanda only), which is less than 10% of total blood volume generally recommended as a maximum volume to be taken over 8 weeks.. At the Niger site ONLY, where an additional 1 mL sample will be collected within a random time window between D0 & D7, the maximum blood volume will be approximately **49.5 mL**.

The maximum blood volume that will be drawn in children below the age of 12 is **17.5 ml** in the first 24 hours of the study. This is below the 3 ml/kg in the first 24 hours as recommended only if

the subjects are ≥ 6 kg [25]. Accordingly, samples collected from children of <6 kg will only be those which are specifically required for the efficacy, safety and tolerability assessments, viz., blood smears, dried blood spots, venous samples for clinical biochemistry, haematology and PK samples.

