Blood smear (*)	0.5	0.5 (Hb, Hct only if FBC not done)		0.5		0.5	0.5	0.5			0.5							0.5 (Hb, Hct only if FBC not done)				0.5 (Hb, Hct only if FBC not done)		0.5	0.5		0.5 (Hb, Hct only if FBC not done)	0.5	0.5	0.5	0.5	0.5	0.5	0.5	(*)	9.5
HCT (EDTA)																																				
Hb (EDTA)																																				
Dried Blood Spot (EDTA) (aliquot of blood collected for microscopy)																																			0	
In vitro/ex vivo sensitivity assays (Heparinized)		2																																2	4	
DNA/RNA/Immunological assessments (EDTA/Heparin)		5		1		1		1				1											1	1	1	1	1	1	1				5	21		
PK sampling (**)		1		1				1					0.5			0.5							1	1		1						1	8			
Biochemistry (heparinised blood)		1																	1				1			1								4		
Full blood count (EDTA)		0.5																				0.5				0.5								2		
Total volumes per time point (ml)	0.5	10	0	2.5	0	1.5	0.5	2.5	0	0	0.5	0	1.5	0.5	0	0	0.5	0	3	0	0	0	4	1.5	2.5	3	2.5	1.5	0.5	0.5	0.5	8.5	0	48.5		

* Patients with >5000 parasites/ μ L at inclusion will have blood smears at 6h, 12h, 18h, 24h and thereafter every 12 hours until parasite clearance (when two consecutive blood smears are negative) even if blood smears stay positive longer than 72h. In all cases, blood smears must be collected at 24h, 48h, 72h and then at all visits, including unscheduled visits. If parasitemia <=5000 parasites/ μ L at inclusion, blood smears must still be performed at 24h, 48, and 72h.

** Day 0, day 7 and day of recurrence samples will be obtained in all subjects. In 500 subjects, two samples will be taken at a random timepoint in the first 72 hours and two samples will be taken at a random timepoint in the first 42 days. In NIGER ONLY, an additional sample of 1 mL will be collected at a random timepoint between D0H0 & D7 from all subjects included at the site. Accordingly, the maximum blood volume from children recruited at the NIGER SITE ONLY will be 49.5 mL.

PK samples have been included in this table to calculate the total volume of blood to be collected but may not be collected at the time-points indicated on this table (e.g., H6, H64, D21, D35 PK samples). An additional PK sample of 1 mL will be collected at H52 or at H64 but has been included in this table as 0.5 mL at both time-points, again to calculate the total volume.

DeTACT-Africa project blood sampling schedule (For Gambia, Rwanda sites only: Subjects \geq 12 years)																																				

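### The blood-volume maxima in Protocol 9.10 omit the QTc-triggered PK samples; after an abnormal H4 ECG, full sampling can exceed the protocol's own 3 mL/kg limit just above 6 kg

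*Protocol*

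**What the plan says.** Protocol 9.10 states that the maximum for children under 12 "is 17.5 ml in the first 24 hours of the study". It then compares that volume with a per-kilogram limit: "This is below the 3 ml/kg in the first 24 hours as recommended only if" the child is 6 kg or heavier. Below that weight, sampling is cut back: "Accordingly, samples collected from children of <6 kg will only be those which are specifically required for the efficacy, safety and tolerability assessments". The samples kept for these children include the PK samples.

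The same section gives 63-day maxima of about 48.5 mL for children, 49.5 mL in Niger, and 66.5 mL for participants aged 12 and over in The Gambia and Rwanda. It describes the maximum as the case in which every sample is taken, the child is in the PK and other subsets, and there is one recurrence and/or unscheduled visit.

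Section 9.6 requires further drug-level samples when an abnormal QT/QTc is found, and again 6 and 12 hours later. Section 9.7.5 repeats this. It asks for a sample on first identification at H4 or D42, and for samples "At 6 and 12 hours after the first abnormal QT/QTc interval at any time-point (H4, H52, H64, D42"), up to 3 mL. The same list in 9.7.5 includes the PK sample on the day of a recurrence.

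For Niger, 9.7.5 says that "three random samples during the first 3 days of dosing will be collected" in all patients. Section 9.10 and the Appendix 1 footnote instead place the additional Niger sample between D0 and D7.

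**The concern.** The 17.5 mL figure is what justifies full sampling from 6 kg. At that weight the 3 mL/kg limit is 18.0 mL, so the spare volume is 0.5 mL. Any required 1 mL sample missing from the sum uses up that margin. The QTc-triggered samples are required whenever the ECG criterion is met, and after an abnormal H4 ECG they come at about H4, H10 and H16. A child of just over 6 kg could then give more than the protocol's own limit while every instruction is followed, and no written rule would prevent it. Children of this size can be enrolled: entry is from 6 months of age and the dosing bands start at 5 kg. What is at stake is the accuracy of a stated safety figure and the cut-off that rests on it. No efficacy or safety comparison is affected.

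**Working it through.** **Inputs.** Volumes by time point are from the children's table in Appendix 1. The limit and cut-off are from Protocol 9.10, the QTc samples from 9.6 and 9.7.5, and the Niger sample from 9.7.5, 9.10 and Appendix 1.

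**Step 1: reproduce the stated figures.**
- First 24 hours: SCR 0.5 + H0 10 + H4 0 + H6 2.5 + H8 0 + H12 1.5 + H18 0.5 + H24 2.5 = 17.5 mL. This matches exactly. 17.5 / 6 = 2.92 mL/kg.
- 63 days, children, by row: 9.5 + 4 + 21 + 8 + 4 + 2 = 48.5 mL. Age 12 and over: 9.5 + 6 + 37 + 8 + 4 + 2 = 66.5 mL. Both match.

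**Step 2: see what the PK row contains.** H0 1 + H6 1 + H24 1 + H52 0.5 + H64 0.5 + D7 1 + D21 1 + D35 1 + recurrence 1 = 8 mL. The recurrence sample is counted. No QTc-triggered sample is, and the H4 column is 0 mL.

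**Step 3: add the omitted samples to the 24-hour figure.** Lowest weight within the limit = volume / 3.

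| Case | Volume (mL) | mL/kg at 6 kg | Lowest weight within limit (kg) |
|---|---|---|---|
| As stated | 17.5 | 2.92 | 5.83 |
| Abnormal QTc at H4 (+3) | 20.5 | 3.42 | 6.83 |
| Niger third random sample (+1) | 18.5 | 3.08 | 6.17 |
| Both (+4) | 21.5 | 3.58 | 7.17 |

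The Niger rows assume that all three random samples fall in the first 24 hours. Appendix 1 already places both standard random samples at H6 and H24.

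**Step 4: vary the counting convention.** The limit at 6 kg is 18.0 mL.

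| Convention | QTc at H4 (mL) | Niger alone (mL) |
|---|---|---|
| Protocol's own count | 20.5, over | 18.5, over |
| Without the screening draw (-0.5) | 20.0, over | 18.0, at limit |
| Without the H24 draw except its PK sample (-1.5) | 19.0, over | 17.0, within |
| Without both (-2.0) | 18.5, over | 16.5, within |

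**Step 5: vary which optional samples are drawn, with QTc samples at H4.**
- Child outside the 500-patient random PK subset: 17.5 - 2 + 3 = 18.5 mL, over.
- Site without ex vivo culture: 17.5 - 2 + 3 = 18.5 mL, over.
- Site without the H6, H12 and H24 DNA/RNA draws: 17.5 - 3 + 3 = 17.5 mL, within.

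**Step 6: children under 6 kg.** Six smear draws of 0.5 mL, three PK samples of 1 mL, biochemistry 1 mL and full blood count 0.5 mL give 3 + 3 + 1 + 0.5 = 7.5 mL. With both additions this is 7.5 + 4 = 11.5 mL, or 11.5 / 5 = 2.3 mL/kg at 5 kg, within the limit.

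**Step 7: 63-day maxima with QTc samples.** Children 48.5 + 3 = 51.5 mL; Niger 49.5 + 3 = 52.5 mL; age 12 and over 66.5 + 3 = 69.5 mL. These apply to a first abnormality at H4 or D42. If it is first seen at H52 or H64, the fixed PK sample is already counted, so only 2 mL is added, and outside the first 24 hours.

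**The case against.** The best defence is that nothing was added up wrongly. Every total reproduces, 9.10 lists the contingencies its maximum covers, and a QTc event is not among them. That stands as far as the sums go. It does not explain why one conditional PK sample (recurrence) is counted and the others on the same list in 9.7.5 are not, when the text describes a maximum with all samples taken.

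The second defence is rarity, and it stands. The case needs QT/QTc above 500 ms at H4 in a child of about 6 to 7 kg with most optional samples drawn. Several of those are taken only at some sites, the admission DNA/RNA volume is an upper bound, and section 3.2 describes QTc prolongation as having low incidence.

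Three stronger readings are tempting and should not be made.
- **That the protocol breaches its limit in its smallest children.** Those under 6 kg are on reduced sampling and stay within it (step 6). Only a narrow band above 6 kg is affected.
- **That Niger's third sample breaches the limit by itself.** The excess is 0.5 mL, for 6.0 to below 6.17 kg. It needs all three random samples within 24 hours and disappears under three of the four conventions in step 4.
- **That the 63-day claim, "which is less than 10% of total blood volume generally recommended as a maximum volume", also fails.** This needs a blood volume per kilogram that the documents do not give. At 6 kg, 48.5 mL is under 10% only above 48.5 / (0.1 × 6) = 80.8 mL/kg. Over an assumed 70 to 85 mL/kg, the lowest weight that satisfies the claim runs from 6.93 down to 5.71 kg, on both sides of 6 kg. The answer is set by the assumption.

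**Conclusion.** The point holds in limited form. The stated 24-hour and 63-day maxima omit required QTc-triggered PK samples of up to 3 mL. After an abnormal H4 ECG the 24-hour total is 20.5 mL, which exceeds 3 mL/kg for children from 6.0 to just under 6.83 kg when all optional samples are drawn. The excess at 6 kg persists under all four counting conventions, but not at a site that omits the H6, H12 and H24 DNA/RNA draws.

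The Niger point is secondary. The extra sample is in the 63-day total but has no 24-hour figure (up to 18.5 mL, or 21.5 mL with QTc samples, if all three random samples fall in the first 24 hours), and its window differs between sections.

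This is a minor finding because very few infants could be affected. It deserves correction because the 6 kg cut-off rests on the figure.

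**What to change.** 1. Restate the maxima with these samples included. First 24 hours, children: 20.5 mL, Niger 21.5 mL. 63 days: 51.5 mL for children, 52.5 mL in Niger, 69.5 mL for age 12 and over.
2. Reconcile the two windows for Niger's third random sample: the first 3 days in 9.7.5, against D0 to D7 in 9.10 and Appendix 1.
3. Reconcile the weight cut-off for optional sampling with the protocol's own 3 mL/kg limit. One option is to state that optional DNA/RNA draws still outstanding after H4 (H6, H12 and H24, 1 mL each) are omitted when QTc samples are taken. Omitting all three gives 20.5 - 3 = 17.5 mL outside Niger. In Niger it gives 21.5 - 3 = 18.5 mL if all three random samples fall in the first 24 hours, so that site needs its own statement. Cutting the culture sample or the 5 mL DNA/RNA draw would not work, because both are taken at H0, before any H4 ECG.

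The cost is a few restated figures and, under this option, a few optional laboratory samples in very few infants. No sample that 9.10 lists as required for efficacy, safety or tolerability is lost.
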